3.5 Data analyses

The statistical software package SPSS (IBM) will be used for analyses of quantitative data (i.e., survey data, MPS data and frequency data from patient journals). These analyses will include descriptive statistics (to describe the samples) and statistical techniques to look for changes and differences in the study variables within and between the intervention- and the control group throughout the project period - e.g., t-tests and analysis of variance (ANOVA)

tests. We hypothesize that SmartJournal usage will lead to favorable changes in variable scores. In caregivers: increased scores on the measured COM-B components (survey data). In residents: improved oral health as measured by MPS. In patient journals: increased reporting of oral health related issues. Additionally, regression analysis may be employed to investigate associations between study variables while adjusting for potential covariates (e.g., age, gender, educational level, medical conditions and prescribed medication). NVivo (Alfasoft) will be used as a tool in content analysis of oral health-related reports in patients journals. These analyses will (qualitatively) describe potential differences and changes in such reports within and between the intervention- and the control group throughout the project period.

4. Ethics and privacy

The SmartJournal intervention aims to assist non-dental care providers with preserving nursing home residents' statutory right to good oral hygiene and necessary dental treatment. Respect for the individual's intrinsic value, self-determination and situation pervades the development and anticipated use of the tool. The project is guided by the intentions of the Declaration of Helsinki and ethical guidelines provided by the Norwegian National Research Ethics Committees. Informed consent will be obtained from nursing home caregivers and residents before data collection. Consent forms are designed in accordance with the templates for information material provided by Sikt – Norwegian Agency for Shared Services in Education and Research, and Regional Committees for Medical and Health Research Ethics. Nursing home residents constitute a vulnerable group in which many individuals may have reduced decision-making capacity, and thereby, difficulties giving free and informed consent to being subjects of research. However, since the overall aim with the SmartJournal intervention is to assist health personnel with preserving oral health in this particular group, it is essential to include them in the research. Therefore, if residents have reduced decision-making capacity, deputy consent will be obtained from their next of kin. Data registered in SmartJournal (i.e., data for residents included in the intervention group) will be transferred to a research database at the University of Stavanger. At the SmartJournal login site, health personnel are asked to enter three codes: one code for the nursing home, one (personal) caregiver code and one (personal) resident code. The codes for caregivers and residents will be listed in an identification key which is only available to authorized project staff. At the end of the project, data will be deidentified and it will not be possible for anyone to link any information to individual participants. Data obtained from questionnaires, clinical assessments (MPS) and patient journals are registered with the same, individual codes as for data registered in SmartJournal, which makes it possible to link data obtained from all sources. Extractions from the UiS database and data from questionnaires will be stored in a highly secured data system at the Oral Health Centre of Expertise Rogaland. Only authorized project staff will have access to the data.

5. Contributions

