
¹ Prosthetic devices include all forms of removable dentures and fixed prosthodontics.

from the interventions ‘Managing Oral Hygiene Using Threat Reduction’ (‘MOUTH’) [27,28] and ‘Mouth Care Without a Battle’ (MCWB) [29]. The content in this part of the tool is illustrated with photos and figures and includes a video with recommendations on how to handle situations where patients refuse oral care assistance. Acceptability of the SmartJournal prototype has been tested in a feasibility study which has already been notified to, and approved by, the Regional Committee for Medical and Health Research Ethics (REK 2020/31294) and the Norwegian Centre for Research Data (NSD). Preliminary results from this study indicates that SmartJournal is well accepted among its users: According to survey data collected from caregivers employed at three nursing homes in Rogaland, Norway (n=86), 72% reported that SmartJournal is a useful tool, 94% reported that it is easy to use and 69% reported that they would like to use a refined version of the tool in the future.

2. Study objectives

Since SmartJournal seems to be well accepted among its potential users, the present study aims to evaluate *effects* of its usage. Thus, the objectives of the current research are to assess 1) the effectiveness of SmartJournal in enhancing nursing home caregivers' capability, opportunity, motivation and routines related to oral care tasks, 2) whether SmartJournal usage may result in improved oral health for nursing home residents and 3) whether SmartJournal usage may result in changes in the documentation of oral health related issues in patient journals.

3. Methods

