3.2 Design and recruitment

A pragmatic cluster randomized controlled trial (C-RCT) [34] will be employed to assess effects of SmartJournal usage as specified under study objectives. Public nursing homes located in the southern part of Rogaland county, Norway, will be recruited and randomly assigned to an intervention group and a control group. Institutions housing long-term residents will be included, while institutions with primarily short-term residents, institutions already following a specific protocol for oral care and/or participate in other comprehensive interventions are excluded. Nursing homes in the intervention group will be provided with

² NSCC: National and international collaboration arena for large and small companies, municipalities, hospitals, public organizations, user organizations, academia / R&D institutions and investors. The cluster works to develop sustainable health solutions for the future (<https://www.smartcarecluster.no/english/about-us>).

tablets containing SmartJournal, while nursing homes in the control group will continue with existing oral care routines. The intervention will last for 12 weeks. Measurements will be performed at baseline, 3 months and 9 months.

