Strategies used for recruitment of individual participants (caregivers and residents), and procedures for delivery of the intervention, will be similar to those used in the feasibility study since they proved to be successful: resource groups, comprised of heads of wards and selected health personnel, will be established at each of the included nursing homes. Meetings will be scheduled to adapt delivery of the project to each individual institutions' resources and facilities, and members of the resource groups will be assigned the task of recruiting individual participants. Written informed consent will be requested for both residents and caregivers to be enrolled in the study. Nursing home residents constitutes a vulnerable group in which many individuals may have reduced decision-making capacity. For these individuals, deputy consent will be obtained from their next of kin. Residents receiving end-of-life palliative care are excluded. Both full- and parttime nursing staff will be included. Health personnel with purely administrative tasks (i.e., heads of institutions) are excluded. Following recruitment of participants and baseline measurements, nursing homes in the intervention group will be provided with SmartJournal toolboxes and packages with oral hygiene equipment, while nursing homes in the control group will receive oral hygiene equipment packages only. The SmartJournal toolboxes include tablets with SmartJournal installed, antibacterial touchscreen wipes, flashlights for monthly oral inspections, an instruction video, an instruction book and SmartJournal information posters. The oral hygiene equipment packages include toothbrushes for permanent teeth and prosthetic devices, dental floss, interdental brushes, toothpaste and inspection mirrors. Training, follow-up and technical support for SmartJournal users will be provided by project staff employed at the Oral Health Centre of Expertise Rogaland.

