3.3 Measurements

The effectiveness of SmartJournal in enhancing nursing home caregivers' capability, opportunity, motivation and routines related to oral care tasks will be measured by a survey questionnaire capturing components of the COM-B model [26]. Caregivers in both the intervention- and the control group will be asked to fill out the survey questionnaire three times: at baseline, 3 months and 9 months.

Effects of SmartJournal usage on nursing home residents' oral health will be assessed using the mucosal-plaque score (MPS) (21) as a primary outcome measure. MPS is comprised of a four-point plaque score (PS) and a four-point mucosal score (MS). PS = 1: no visible plaque, PS = 2: plaque is barely visible, PS = 3: moderate amount of plaque, PS = 4: large amount of plaque almost covering the whole surface of teeth. MS = 1: normal mucosa, MS = 2: mild inflammation, MS = 3: medium inflammation, MS = 4: strong inflammation. For both scores, if in doubt between 1 and 2, dental personnel are instructed to score 1. If in doubt between 3 and 4, they are instructed to score 4. The index is designed to evaluate oral health and oral hygiene in groups of individuals. This makes it a suitable index to be used when conditions

are not optimal to assess the patient's oral health. In a nursing home setting, dental personnel have limited equipment and poor light compared to an ordinary dental clinic setting. Therefore, using an index designed to be applied outside a dental clinic setting is feasible in this context. Residents in both the intervention- and the control group will have MPS assessment at three times: at baseline, 3 months and 9 months. MPS assessments will be performed by dental professionals employed at the Oral Health Center of Expertise Rogaland, Norway. Calibration will be undertaken to ensure reliability of the clinical measurements.

Effects of SmartJournal usage on documentation of oral health related issues in patient journals will be measured both quantitatively (i.e., frequency of documentation) and qualitatively (i.e., qualitative assessment of documentation) at three times throughout the project period: at baseline, 3 months and 9 months. Additional journal data shown to be associated with oral health will also be retrieved and used to describe the study sample and to be included as covariates in statistical analyses. These data include socio-demographics, medical conditions and prescribed medication.

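### Section 3.5 names t-tests and ANOVA within and between arms, without making the between-arm MPS contrast decisive or allowing for randomisation by nursing home

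*Protocol*

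**What the plan says.** Protocol section 3.5 (Data analyses) plans "statistical techniques to look for changes and differences in the study variables within and between the intervention- and the control group" and gives t-tests and ANOVA as examples. It does not rank the within-arm and between-arm comparisons. Regression is optional, is aimed at associations between study variables, and does not list baseline MPS among its example covariates.

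The hypothesis follows in the same section: "We hypothesize that SmartJournal usage will lead to favorable changes in variable scores". For residents it reads "In residents: improved oral health as measured by MPS". Objective 2 in section 2 asks "whether SmartJournal usage may result in improved oral health for nursing home residents". None of these names the control arm.

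Section 3.2 sets up a cluster randomised controlled trial. It first says that "nursing homes in the control group will continue with existing oral care routines". On what is handed out after baseline, it says that "nursing homes in the intervention group will be provided with SmartJournal toolboxes and packages with oral hygiene equipment". Its statement for the comparison arm is that "nursing homes in the control group will receive oral hygiene equipment packages only". Section 3.3 makes MPS the primary outcome measure and adds: "Residents in both the intervention- and the control group will have MPS assessment at three times: at baseline, 3 months and 9 months".

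Section 3.4 plans 12 homes of 30 residents, 180 per arm, with 33% drop-out. It gives no intracluster correlation (ICC).

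**The concern.** Two weaknesses meet in the same sentence of section 3.5.

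The first is the contrast. New equipment and repeated examination by dental staff could improve MPS in both arms. A before-after change in the SmartJournal arm then mixes those influences with any effect of the tool. The difference between randomised arms removes what they share. Section 3.5 plans both kinds of test and does not say which one carries the conclusion on residents' oral health.

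The second is the method. Homes are randomised, not residents. A t-test or ANOVA that treats residents as independent understates the standard error of the arm difference, so even the right contrast can be significant too often. With only 12 homes, the degrees of freedom matter as well. Baseline MPS is collected on every assessed resident, but the named tests do not adjust for it; an analysis of change uses it by subtraction only.

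**Working it through.** The protocol states no false-positive rate, so there is no figure of its own to reproduce on this point.

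**Inputs from the protocol (section 3.4).** 180 residents per arm in 6 homes of 30, with 33% loss: 180 × 0.67 = 120.6, taken as 120 completers per arm, or 6 homes of 20.

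**Assumptions (no values in the protocol).** MPS change is analysed as a score. The baseline to follow-up correlation is r = 0.5, so the SD of change is √(2(1 − r)) = 1 baseline SD. The ICC of change is 0, 0.01, 0.05 or 0.10. Both arms improve by the same 0.3 SD and the true arm difference is zero.

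**Step 1: plain between-arm t-test.**
- Design effect DE = 1 + (20 − 1) × ICC = 1, 1.19, 1.95, 2.90.
- The statistic has variance of about DE instead of 1, so its false-positive rate is 2 × (1 − Φ(1.96/√DE)).
- A t-test on the 12 home means has 12 − 2 = 10 degrees of freedom. In simulation (40,000 trials per ICC) it is significant in about 0.05 at every ICC.

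**Step 2: paired test within the SmartJournal arm, ignoring clustering.**
- λ = 0.3 × √120 / 1 = 3.286.
- The probability of significance is p ≈ Φ((λ − 1.96)/√DE) + Φ((−λ − 1.96)/√DE). This gives 0.888, 0.829 and 0.783 at ICC 0.01, 0.05 and 0.10. At ICC 0 it is 0.908, or 0.903 with t on 119 degrees of freedom; the latter is used below.

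**Step 3: both arms tested, as section 3.5 plans.** The arms are independent and share the same p, so both are significant with probability p², and the SmartJournal arm alone with probability p(1 − p).

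| ICC (assumed) | Plain between-arm test falsely significant | SmartJournal arm significant, p | Both arms significant, p² | SmartJournal arm only, p(1 − p) |
|---|---|---|---|---|
| 0 | 0.05 | 0.90 | 0.82 | 0.09 |
| 0.01 | 0.07 | 0.89 | 0.79 | 0.10 |
| 0.05 | 0.16 | 0.83 | 0.69 | 0.14 |
| 0.10 | 0.25 | 0.78 | 0.61 | 0.17 |

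Simulation agrees with every column to within about 0.01. With a smaller shared improvement of 0.2 SD and no clustering, the SmartJournal-only pattern occurs in about 0.24 of trials.

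**Step 4: what baseline adjustment might gain.**
- For home means of 20 residents, the variance ratio of adjusted to follow-up-only is [ICC(1 − r_b²) + (1 − ICC)(1 − r_w²)/20] / [ICC + (1 − ICC)/20], where r_b is the home-level and r_w the resident-level correlation.
- At ICC 0.05 and r_w = 0.5 it is (0.05 + 0.0356)/0.0975 = 0.88 for r_b = 0.
- For r_b = 0.8 it is (0.018 + 0.0356)/0.0975 = 0.55.
- The protocol gives neither correlation, so the gain could be small or substantial.

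**The case against.** The strongest reply is that the between-arm contrast is already implied. The trial is randomised, and section 3.2 says that design is used to assess effects as set out in the objectives. The hypothesis is causal: an equal improvement in homes without SmartJournal would not show that SmartJournal led to it. Giving equipment to both arms balances it, which suggests that an arm comparison was intended. Section 3.5 does plan that comparison. All of this stands.

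A reader might therefore go too far in inferring that the protocol accepts a within-arm improvement as proof, or that a shared improvement would satisfy the hypothesis. The documents do not support either. Nowhere does the text say that a within-arm test suffices. Because both arms would be tested, a shared improvement would usually be visible: in the scenario above both arms are significant in about 0.82 (ICC 0) to 0.61 (ICC 0.10) of trials. The 0.90 for the SmartJournal arm taken alone is not the error rate of any rule in the protocol.

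It can also be said that t-tests and ANOVA are only examples, and that ranking and model detail often sit in a statistical analysis plan, which is not at hand. That is fair for the unstated ranking, which on its own would be a drafting matter. It does not remove the point on method: the tests the protocol names do not fit a design that randomises 12 homes, and a better analysis is available from data already planned.

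**Conclusion.** The point holds in a limited form. The between-arm contrast is planned and probably intended, but neither the hypothesis nor the analysis section makes it decisive, and shared equipment and assessments mean that a within-arm change cannot stand in for it. The misleading pattern, with only the SmartJournal arm significant and no true arm difference, has a probability of about 0.09 to 0.17 under the assumed 0.3 SD shared improvement.

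The firmer part is the method. If the named between-arm t-test is run on residents as if they were independent, its false-positive rate is about 0.07, 0.16 or 0.25 at ICC 0.01, 0.05 or 0.10, against about 0.05 for an analysis of home means.

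The ICC, correlation and shared improvement are assumptions, and MPS is treated as a score although section 3.4 powers on the proportion with MPS of 2 or more. The figures show what is possible, not how likely it is.

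**What to change.** In section 3.5:
- State that the conclusion on residents' oral health rests on the between-arm difference in follow-up MPS, adjusted for baseline MPS, from a model with a nursing-home random effect and small-sample degrees of freedom for 12 homes.
- Word the resident hypothesis as intervention versus control.
- Report within-arm changes descriptively.

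This needs no new data. There are costs:
- Intervals will be wider than those of the plain test, which are too narrow under clustering. Before any gain from baseline adjustment the factor is about √DE × 2.23/1.97 (t quantiles on 10 and 238 degrees of freedom): 1.2, 1.6 and 1.9 at ICC 0.01, 0.05 and 0.10.
- The model assumes that follow-up MPS is missing at random, which matters with 33% expected loss.
- A home-level baseline term would use one of about 10 degrees of freedom.

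Baseline adjustment is for precision and does not settle which contrast decides; the protocol does not establish how much it would gain with 12 homes.

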3.4 Power calculations and estimation of sample size for clinical outcomes

Experiences from the feasibility study show that resident participation may comprise a challenge due to high rates of morbidity, mortality and CRB in this part of the population. Estimation of sample size is largely reproduced from Overgaard et al. [32] who also used MPS as a primary outcome variable in their study on oral health in nursing home residents. Overgaard et al. based their power calculations on reductions in $MPS \geq 2$ from 60% to 15% as reported by Hede et al. [17]. Like Overgaard et al. we assume an alpha of 0.5, a power of 80% and a 33% drop-out rate due to the residents' frail condition and a median resident time of two years. Using the programme G*Power 3 [35] for power calculations, Overgaard et al. found that at least 92 residents should be included in each group for oral health assessments. A medical statistician has been consulted to further adapt the calculations to the present study setting (taking into account the number of eligible nursing homes and residents in the southern part of Rogaland), recommending the inclusion of 12 nursing homes each with 30 residents opted for oral health assessments. Thus, a total of 360 residents will be included for oral health assessments, 180 in the intervention and control group, respectively. All eligible caregivers in the 12 included nursing homes will be invited to take part in the survey capturing components of the COM-B model as described in the Measurements section (4.2). Experiences from the feasibility study indicate that this broad inclusion strategy, along with assigning the recruitment task to members of the institutions' resource groups, foster a sense of community regarding project participation. This may, in turn, motivate institutions and individual participants to remain part of the project throughout the study period.

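### If the ANOVA named in Protocol 3.5 is a three-visit repeated-measures ANOVA, residents without a 9-month MPS also lose their 3-month score; a mixed model on all assessments avoids this

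*Protocol*

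**What the plan says.** Protocol section 3.3 makes MPS a primary outcome measure and sets three visits: "Residents in both the intervention- and the control group will have MPS assessment at three times: at baseline, 3 months and 9 months". Section 4 says that clinical, journal, questionnaire and app data carry the same individual codes and can be linked, so these are repeated measurements on the same residents.

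Section 3.4 plans 12 nursing homes with 30 residents each, 360 in total and 180 per arm. It assumes "a 33% drop-out rate due to the residents' frail condition and a median resident time of two years", without saying over what period the 33% applies.

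Section 3.5 names SPSS and plans "statistical techniques to look for changes and differences in the study variables within and between the intervention- and the control group throughout the project period". T-tests and ANOVA are given as examples, and the type of ANOVA is left open. Regression is optional and is described as a way to study associations with covariate adjustment. No named method is described as combining all available visits in one analysis.

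**The concern.** The intervention lasts 12 weeks, so the 3-month visit falls at its end. A classical repeated-measures ANOVA over three visits needs a complete row for each resident. A resident who is examined at baseline and 3 months, and then dies or cannot be examined at 9 months, leaves the analysis entirely.

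In that analysis the 3-month contrast would rest only on residents still alive and examinable six months later. That selects on an event after randomisation and discards valid outcome data. The loss is unlikely to be random: section 3.4 gives morbidity, mortality and care-resistant behaviour as obstacles to participation, and the introduction links such behaviour to poor oral hygiene. The residents kept would tend to be the healthier and more cooperative ones.

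**Working it through.** **The plan's own figures.** 12 × 30 = 360 residents, and 360 / 2 = 180 per arm, as stated. The 92 per group that section 3.4 takes from a cited trial could not be reproduced from the printed rates and drop-out. That is a separate matter, and 92 is not used below.

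**Which ANOVA.** With two arms, a one-way ANOVA at a single visit only repeats the independent t-test (F = t²). ANOVA adds something to the t-tests here mainly if visit is a factor. For change within and between two arms over three visits, that points to a group-by-time repeated-measures ANOVA. This is an inference, because the document does not say it.

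**Which residents each method keeps.**
- Independent t-test at 3 months: everyone with a 3-month score.
- Paired t-test, baseline to 3 months: everyone with those two scores.
- Between-arm ANOVA at 3 months, or of change to 3 months: the same residents as the corresponding t-test.
- Three-level repeated-measures ANOVA with listwise deletion: only residents with all three scores.

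One simulated data set of 360 residents, with expected loss of 12.5% by 3 months and 33% by 9 months, illustrates this. Both 3-month t-tests kept 312 residents and the repeated-measures ANOVA kept 234.

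**Expected numbers.** Assumption: the 33% is cumulative loss by 9 months.
- Residents with all visits: 360 × (1 − 0.33) = 241.2, about 241 (about 121 per arm).
- Seen at 3 months under constant hazard: 0.67^(3/9) = 0.875, and 360 × 0.875 = 315.0 (about 158 per arm).
- Observed 3-month scores discarded: 315.0 − 241.2 = 73.8, about 74 (about 37 per arm). As a share, 73.8 / 315.0 = 23%.

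**Range by timing of loss.**

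| Share of the loss before 3 months | Seen at 3 months | 3-month scores discarded |
|---|---|---|
| All | 241 | 0 |
| Half | 360 × (1 − 0.165) = 301 | 59 |
| None | 360 | 360 × 0.33 = 119 |

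**Cross-check from the two-year median stay alone**, at constant hazard and per arm:
- At 3 months: 180 × 0.5^(3/24) = 165.1.
- At 9 months: 180 × 0.5^(9/24) = 138.8.
- Discarded: 165.1 − 138.8 = 26.3 per arm.

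**Effect on precision** of a simple 3-month comparison, under constant hazard and the 33%:
- Ignoring clustering: √(157.5 / 120.6) = 1.143, a standard error about 14% larger.
- With an ICC of 0.05 (an assumption; the protocol gives none) and six homes per arm, the home sizes are 26.25 and 20.1. The design effects are 1 + 25.25 × 0.05 = 2.2625 and 1 + 19.1 × 0.05 = 1.955. Effective numbers are 157.5 / 2.2625 = 69.6 and 120.6 / 1.955 = 61.7, and √(69.6 / 61.7) = 1.062, about 6% larger.

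**The case against.** The strongest reply is that section 3.5 commits to very little. The tests are only examples, repeated-measures ANOVA is not named, and no complete-case rule is stated. How missing visits are handled is commonly left to the statistical analysis plan, which is not at hand, and nothing in the protocol prevents a mixed model in SPSS. All of this stands. It makes the point conditional, and the absence of a missing-data section is not the finding.

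Four stronger readings are tempting, and the document does not support them:
- A reader might infer that the t-tests also lose residents who leave after 3 months. They do not, because they use one or two visits.
- A reader might infer that the protocol plans a complete-case analysis. It does not say so, and an ANOVA at each visit would keep these residents.
- A reader might take the 33% as loss between 3 and 9 months. Section 3.4 ties it to no time point and uses it as an input to sample size, so drop-out was foreseen at the design stage.
- A reader might extend the figures to the caregiver survey. The 33% rests on residents' frailty and length of stay, and no attrition figure is given for caregivers.

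The objection does not remove the choice of method. The techniques that are named either drop incomplete residents or, if run visit by visit, compare different sets of residents at each visit and leave the 3-month scores unused in the 9-month contrast. A better method is available in the same software.

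**Conclusion.** The point holds in conditional form, as an inexpensive improvement to the named method. If the ANOVA is the classical three-visit repeated-measures form, about 241 of 360 residents would be analysed. About 74 observed 3-month MPS scores would be discarded under constant hazard, with a range of 0 to 119.

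These figures rest on three assumptions: the type of ANOVA, the 33% being cumulative loss by 9 months, and the timing of loss within that period. The cost in precision is modest, about 6% to 14% on the standard error under the assumptions shown. The weightier issue is selection, since the contrast at the end of the intervention would depend on who can still be examined six months later. The size and direction of any resulting bias in the treatment contrast cannot be derived from the document.

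**What to change.** In Protocol section 3.5, name for MPS a linear mixed model (SPSS MIXED) with arm, visit and arm-by-visit as fixed effects and random effects for nursing home and resident, fitted to every available assessment. Add that values already recorded stay in the analysis after a resident is later lost. The 3-month and 9-month contrasts then come from one model, and a resident seen at baseline and 3 months contributes to the 3-month contrast.

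The cost is a change of wording; software, visits and data stay as they are. The drawback is that the model assumes missingness is explained by observed values. With loss driven by frailty and care resistance that may fail, so a brief sensitivity check should be named with it. The same model can serve the caregiver scores, although the protocol gives no attrition figure from which to size the gain there.

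### Nursing homes are randomised, but the only tests named in section 3.5 take no account of nursing home

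*Protocol*

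**What the plan says.** Protocol section 3.2 describes a cluster randomised trial in which public nursing homes "will be recruited and randomly assigned to an intervention group and a control group". Section 3.4 reports a statistician's advice "recommending the inclusion of 12 nursing homes each with 30 residents opted for oral health assessments", so that "a total of 360 residents will be included for oral health assessments, 180 in the intervention and control group, respectively". Section 3.3 makes the mucosal-plaque score (MPS) the primary outcome for residents' oral health. It is scored on each resident: "Residents in both the intervention- and the control group will have MPS assessment at three times: at baseline, 3 months and 9 months".

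Section 3.5 covers the survey, MPS and journal-frequency data together. It promises "statistical techniques to look for changes and differences in the study variables within and between the intervention- and the control group", with the examples "e.g., t-tests and analysis of variance (ANOVA"). A regression is optional, "adjusting for potential covariates (e.g., age, gender, educational level, medical conditions and prescribed medication").

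The protocol mentions no mixed or multilevel model, generalised estimating equations, cluster-robust standard error, home-level summary, ICC or design effect. Nursing home appears as the unit randomised, in the sample-size count and as a login code (section 4), but never as a term in an analysis.

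**The concern.** Residents of one home share staff, routines and equipment, so their scores tend to be alike. The comparison between groups rests on 12 randomised units, not on 360 independent residents. A t-test or ANOVA on residents treats variation between homes as if it were noise between independent people, which makes the standard error and the p-value too small. A significant MPS difference could then reflect which homes fell into which group.

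The test families are not wrong in themselves: a t-test on the 12 home means would be valid. The fault is that the unit of analysis is not stated. Because MPS is scored per resident and the sample is counted in residents, the natural reading is a resident-level test. Caregivers and patient journals are also grouped within homes, so the same gap affects those outcomes.

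**Working it through.** **Inputs from the protocol.** 12 homes × 30 residents = 360, or 180 per group, which agrees with section 3.4. 180 / 30 = 6 homes per group (implied, not stated). With 33% drop-out, 30 × 0.67 = 20.1, so about 20 analysed residents per home.

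**Assumptions.** Two-sided 5% level (section 3.4 prints alpha as 0.5, which is a separate matter); ICC of 0.02 to 0.10, as the protocol gives none; no true effect; equal home sizes; tests run on residents.

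**Single time point.** With m residents per home:

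- Design effect DE = 1 + (m − 1) × ICC.
- True type I error of the resident-level test ≈ 2 × (1 − Φ(1.96 / √DE)).
- Ratio of the correct to the resident-level interval width = √DE × t(10 df) / t(resident df), both at 97.5%. Here t(10 df) = 2.228; the resident-level value is 1.970 for m = 20 (238 df) and 1.967 for m = 30 (358 df).

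Example, m = 20 and ICC 0.05: DE = 1 + 19 × 0.05 = 1.95; 1.96 / √1.95 = 1.40; type I error 16.0%; width ratio 1.396 × 2.228 / 1.970 = 1.58.

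| m | ICC | DE | Type I error, formula | Type I error, simulated | Width ratio |
|---|---|---|---|---|---|
| 20 | 0.02 | 1.38 | 9.5% | 9.4% | 1.33 |
| 20 | 0.05 | 1.95 | 16.0% | 16.3% | 1.58 |
| 20 | 0.10 | 2.90 | 25.0% | 25.1% | 1.93 |
| 30 | 0.02 | 1.58 | 11.9% | 11.9% | 1.42 |
| 30 | 0.05 | 2.45 | 21.0% | 21.4% | 1.77 |
| 30 | 0.10 | 3.90 | 32.1% | 32.3% | 2.24 |

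The simulated column uses 20,000 null trials per setting.

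**Change from baseline.** Section 3.5 also speaks of changes, and subtracting baseline removes whatever part of a home's level is stable. Let s be the share of between-home variance that is stable over time, and assume a correlation of 0.5 between a resident's two scores within a home. With total variance 1 at each time:

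- Between-home variance of change = 2 × ICC × (1 − s).
- Within-home variance of change = 2 × (1 − ICC) × (1 − 0.5) = 1 − ICC.
- The ICC of change is the first divided by their sum, and goes into the same DE formula.

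Example, ICC 0.10 and s = 0.8: 0.04 / (0.04 + 0.90) = 0.0426. For m = 20, DE = 1.81 and the type I error is 14.5%. At s = 0.5 the ICC of change equals the original ICC, so the single-time-point figures return.

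Simulated type I error of the resident-level change test, for ICC 0.02 / 0.05 / 0.10:

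| Stable share s | m = 20 | m = 30 |
|---|---|---|
| 100% | 5.2% / 5.1% / 5.0% | 5.0% / 4.8% / 5.3% |
| 80% | 6.6% / 9.8% / 14.5% | 8.0% / 12.2% / 19.3% |
| 50% | 9.5% / 16.3% / 25.4% | 12.1% / 21.2% / 32.6% |

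Taking the 0.5 as the overall rather than the within-home correlation moves the 80% row by less than one percentage point.

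**Valid comparator.** A t-test on the 12 home means or mean changes (10 df) rejected in 4.8% to 5.4% of trials in these settings.

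**Caregiver and journal outcomes.** The protocol gives neither cluster sizes nor an ICC for these, so the inflation cannot be sized.

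**The case against.** The strongest reply is that section 3.5 fixes very little. The tests are given as examples, the regression is optional, and a statistical analysis plan that is not at hand may specify a clustered model. An ANOVA can carry home as a random or nested factor.

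The sample size may also already allow for clustering. It derives from an earlier cluster randomised trial, and a statistician gave advice in numbers of homes. Detecting 60% against 15% at two-sided 5% and 80% power needs 17 residents per group (22 with continuity correction), or 26 (33) after dividing by 0.67. The adopted 92 per group leaves 92 × 0.67 = 61.6 after drop-out, which is 3.6 times 17 or 2.8 times 22. That surplus could be an unreported design effect. Finally, every inflation figure rests on an assumed ICC, and a change-score analysis might show no inflation.

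Part of this stands. The examples are not exhaustive, the size is unknown, and the change-score result can be benign. But a larger sample does not correct a test that uses the wrong standard error. The protocol does not leave methods wholly to another document: it names some, and none reflects the design in section 3.2. The benign case needs home differences to be fully stable, which is doubtful when delivery is adapted to each home (section 3.2) and start dates may differ between homes (section 9). For a single-time-point comparison, the direction of the error holds for any positive ICC.

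**Conclusion.** The concern holds and must be fixed before analysis. No method in the protocol accounts for the unit of randomisation, and the natural use of the named tests would overstate the evidence on the residents' primary outcome. At a single time point, the nominal 5% error becomes about 9% to 25% with 20 residents per home and 12% to 32% with 30. Correct intervals are 1.3 to 1.9 and 1.4 to 2.2 times as wide, respectively. For change from baseline, the error runs from 5% to about 25% (20 per home) or 33% (30 per home), depending on how stable home differences are. All of this is conditional on resident-level testing, 6 homes per group and ICCs of 0.02 to 0.10. Confidence is high in the defect and in its direction at a single time point; the actual size cannot be known from the protocol.

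**What to change.** State in section 3.5 that all between-group comparisons account for nursing home, and name the method. Either of these would do:

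1. A mixed model with a random effect for home and a small-sample degrees-of-freedom correction for 12 clusters (Satterthwaite or Kenward-Roger). If the three time points are modelled together, add random effects for person and for home-by-time. Without home-by-time, the group-by-time test behaves like the resident-level change test above.
2. A two-sample t-test on the 12 home means or mean changes, with 10 degrees of freedom.

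Use a matching clustered or home-level analysis for the caregiver scores, and a clustered count model or home-level rates for the journal frequencies.

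The change is to the wording of section 3.5 only, with the same data and the same software. The cost is wider confidence intervals of the correct size.
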